8. INFORMED CONSENT, DATA PROTECTION, TRIAL RECORDS

The trial will be carried out in compliance with the protocol, the principles laid down in the Declaration of Helsinki, in accordance with the ICH Harmonised Tripartite Guideline for Good Clinical Practice (GCP) and relevant BI SOPs.

The Investigator should inform the Sponsor immediately of any urgent safety measures taken to protect the study subjects against any immediate hazard, and also of any serious breaches of the protocol or of ICH GCP.

As a general rule, no trial results should be published prior to finalisation of the CTR.

Insurance Coverage: The terms and conditions of the insurance coverage must be given to each subject and are made available to the Investigator via documentation in the ISF.

8.1 STUDY APPROVAL, SUBJECT INFORMATION, AND INFORMED CONSENT

This trial will be initiated only after all required legal documentation has been reviewed and approved by the respective Institutional Review Board (IRB) / Independent Ethics Committee (IEC) and competent authority (CA) according to national and international regulations. The same applies for the implementation of changes introduced by amendments.

Prior to a subject's participation in the trial, written informed consent must be obtained from each subject (or the subject's legally accepted representative) according to ICH GCP and to the regulatory and legal requirements of the participating country. Each signature must be personally dated by each signatory and the informed consent and any additional subject information form are to be retained by the Investigator as part of the trial records. A copy of the signed and dated written informed consent and any additional subject information must be given to each subject or the subject's legally accepted representative.

The subject must be informed that his/her personal trial-related data will be used by Boehringer Ingelheim in accordance with the local data protection law. The level of disclosure must also be explained to the subject.

The subject must be informed that his or her medical records may be examined by authorised monitors (Clinical Monitor Local/Clinical Research Associate) or Clinical Quality Assurance auditors appointed by Boehringer Ingelheim, by appropriate IRB/IEC members, and by inspectors from regulatory authorities.

8.2 DATA QUALITY ASSURANCE

A quality assurance audit/inspection of this trial may be conducted by the Sponsor or Sponsor's designees, by IRBs/IECs, or by regulatory authorities. The quality assurance auditor will have access to all medical records, the Investigator's trial-related files and correspondence, and the informed consent documentation of this clinical trial.

The data management procedures to ensure the quality of the data are described in detail in the trial data management and analysis plan (TDMAP) available in the TMF.

8.3 RECORDS

CRFs for individual subjects will be provided by the Sponsor. For drug accountability, refer to Section [4.1.8](#).

ClinBaseTM

In the Human Pharmacology Centre – Boehringer Ingelheim's Phase I unit the validated ClinBaseTM system is operated for processing information and controlling data collected in clinical studies. In addition to its function as a procedure control system, ClinBaseTM serves as data base. Instead of being entered into CRFs, selected data are directly entered into the system.

8.3.1 Source documents

Source documents provide evidence for the existence of the subject and substantiate the integrity of the data collected. Source documents are filed at the Investigator's site.

All data reported in the CRFs must be consistent with the source data or the discrepancies must be explained.

Data directly entered into ClinBaseTM (that is, without prior written or electronic record) are considered to be source data. The place where data is entered first will be defined in a trial specific Source Data Agreement. The data in ClinBaseTM are available for inspection at any time.

The Investigator may need to request previous medical records or transfer records, depending on the trial.

8.3.2 Direct access to source data and documents

The Investigator/institution will permit trial-related monitoring, audits, IRB/IEC review and regulatory inspection, providing direct access to all related source data/documents. CRFs and all source documents, including progress notes (if applicable) and copies of laboratory and medical test results must be available at all times for review by the Sponsor's clinical trial monitor, auditor and inspection by health authorities (e.g. FDA). The Clinical Research Associate/on site monitor and auditor may review all CRFs, and written informed consents. The accuracy of the data will be verified by reviewing the documents described in Section 8.3.1.

8.3.3 Storage period of records

Trial site:

The trial site must retain the source and essential documents (including ISF) according to the national or local requirements (whatever is longer) valid at the time of the end of the trial.

Sponsor:

The Sponsor must retain the essential documents according to the Sponsor's SOPs.

8.4 EXPEDITED REPORTING OF ADVERSE EVENTS

BI is responsible to fulfil their legal regulatory reporting obligation and in accordance to the requirements defined in this CTP.

8.6 COMPLETION OF TRIAL

The EC/competent authority in each participating EU member state needs to be notified about the end of the trial (last subject/subject out, unless specified differently in Section [6.2.3](#) of the CTP) or early termination of the trial.

10. APPENDICES

Proprietary confidential information © 2017 Boehringer Ingelheim International GmbH or one or more of its affiliated companies

Proprietary confidential information © 2017 Boehringer Ingelheim International GmbH or one or more of its affiliated companies

11. DESCRIPTION OF GLOBAL AMENDMENT(S)

Number of global amendment	1
Date of CTP revision	01 December 2016
EudraCT number	2016-003047-11
BI Trial number	1407.1
BI Investigational Product(s)	BI 730357
Title of protocol	A partially randomised, single-blind, placebo-controlled trial to investigate safety, tolerability, pharmacokinetics and pharmacodynamics of single rising doses of BI 730357 administered as oral solution and tablets to healthy subjects, and a randomized, open-label, single-dose, three-way cross-over bioavailability comparison of BI 730357 as tablet versus oral solution and tablet with and without food
To be implemented only after approval of the IRB / IEC / Competent Authorities	
To be implemented immediately in order to eliminate hazard – IRB / IEC / Competent Authority to be notified of change with request for approval	
Can be implemented without IRB / IEC / Competent Authority approval as changes involve logistical or administrative aspects only	
Section to be changed	
1. Synopsis, pages 25, 26, 35, 36, 372. Synopsis, pages 49, 583. Page 30
Description of change	
1. Deletion of “50 mg Dose” in the BA part2. Minor editorial changes3. Change of upper age to 45 years (incl)
Rationale for change	
1. To address request by the EC2. Corrections3. To address request by the CA

Proprietary confidential information © 2017 Boehringer Ingelheim International GmbH or one or more of its affiliated companies

Number of global amendment	2
Date of CTP revision	19 January 2017
EudraCT number	2016-003047-11
BI Trial number	1407.1
BI Investigational Product(s)	BI 730357
Title of protocol	A partially randomised, single-blind, placebo-controlled trial to investigate safety, tolerability, pharmacokinetics and pharmacodynamics of single rising doses of BI 730357 administered as oral solution and tablets to healthy subjects, and a randomized, open-label, single-dose, three-way cross-over bioavailability comparison of BI 730357 as tablet versus oral solution and tablet with and without food
To be implemented only after approval of the IRB / IEC / Competent Authorities	
To be implemented immediately in order to eliminate hazard – IRB / IEC / Competent Authority to be notified of change with request for approval	
Can be implemented without IRB / IEC / Competent Authority approval as changes involve logistical or administrative aspects only	
Section to be changed	
 Section 2.1, last paragraph on page 22, line 6 Section 2.1, last paragraph on page 22, line 7 Section 2.1, last paragraph on page 22, line 11 Section 2.3, paragraph 5 on page 24, line 4 Section 3.3.4.2, last paragraph, last line
Description of change	
 ‘132,000’ corrected into ‘1,320,000’ ‘13,200’ corrected into ‘132,000’
Rationale for change	
 Correction of AUC₀₋₂₄ value for male dog at 60 mg/kg/day (from 132,000 to 1,320,000 nM*h) according to Investigator’s Brochure for BI 730357 (Table 5.3:2, page 42, column 4). Correction of AUC₀₋₂₄ values for the maximum acceptable human exposure (from 13,200 to 132,000 nM*h).

Proprietary confidential information © 2017 Boehringer Ingelheim International GmbH or one or more of its affiliated companies

Number of global amendment	3
Date of CTP revision	05 May 2017
EudraCT number	2016-003047-11
BI Trial number	1407.1
BI Investigational Product(s)	BI 730357
Title of protocol	A partially randomised, single-blind, placebo-controlled trial to investigate safety, tolerability, pharmacokinetics and pharmacodynamics of single rising doses of BI 730357 administered as oral solution and tablets to healthy subjects, and a randomized, open-label, single-dose, three-way cross-over bioavailability comparison of BI 730357 as tablet versus oral solution and tablet with and without food
To be implemented only after approval of the IRB / IEC / Competent Authorities	
To be implemented immediately in order to eliminate hazard – IRB / IEC / Competent Authority to be notified of change with request for approval	
Can be implemented without IRB / IEC / Competent Authority approval as changes involve logistical or administrative aspects only	
Section to be changed	
 1. Synopsis, pages 2-3 2. Flow chart for the SRD part, pages 5-6 3. Section 1.2.5, pages 20-24 4. Section 2.1, pages 25, 27, 28 5. Section 2.2, page 28 6. Section 2.3, page 31 7. Section 3.1, page 32 8. Section 3.3, page 35 9. Section 3.3.5, page 40 10. Section 4.1, pages 41-45 11. Section 6.2.2, page 66 12. Section 7.1.3, page 68 13. Section 7.3.2, page 71 14. Section 7.6, page 74

Proprietary confidential information © 2017 Boehringer Ingelheim International GmbH or one or more of its affiliated companies

Number of global amendment	
	3
Description of change	
 Number of subjects in the SRD part increased by 16, administration of 400 mg and 800 mg BI 730357 or placebo under fed conditions added, option for additional subjects removed Visit 3 and standard breakfast added Preliminary clinical data on safety, tolerability and PK from the SRD and BA part presented 800 mg dose added, paragraph to 'maximum dose and dose escalation' amended Fasting conditions specified for SRD part Update on observed half-life Number of subjects increased, option for additional subjects removed, 3 additional dose groups (DGs) added in Table 3.3:1 No replacement for DGs 8, 9 and 10 Number of subjects increased, option for additional subjects removed DGs 8-10 added; maximum dose and number of dose cohorts adapted, DGs 8-10 added in Table 4.1.4: 1, high-fat breakfast and continental breakfast added in the SRD part, composition of standard continental breakfast added (Table 4.1.4:4) Treatments periods of DGs 8-9 described Investigation of dose proportionality under fasting conditions only Investigation of dose proportionality under fasting conditions only Number of subjects in the SRD part increased
Rationale for change	The highest exposures observed in this trial after the 400 mg dose under fasting conditions (C_{max} of 755 nM, AUC_{0-24} of 9,453 nM*h) are significantly below the predicted exposures at 400 mg (C_{max} of 2,547 nM and AUC_{0-24} of 42,458 nM*h) and the acceptable exposure limit of this trial (C_{max} of 5,920 nM, and AUC_{0-24} of 132,400 nM*h). Since we observed a 36% increase in exposure in the fed versus fasted condition, it is planned to investigate 3 additional DGs in the fed condition to further evaluate safety and PK of higher BI 730357 exposures, including the influence of food (normal and high-fat diet) on higher doses. The results will support the testing of higher exposures during the planned multiple-rising dose trial and further clinical development.

APPROVAL / SIGNATURE PAGE

Document Number: c11248385

Technical Version Number: 4.0

Document Name: clinical-trial-protocol-revision-03

2. LIST OF ABBREVIATIONS

Term	Definition / description
ADS	Analysis Dataset
AE	Adverse Event
AESI	Adverse Event of Special Interest
ALT	Alanine Aminotransferase
ANCOVA	Analysis of Covariance
ANOVA	Analysis of Variance
AST	Aspartate Aminotransferase
AUC _{0-∞}	Area under the concentration-time curve of the analyte in plasma over the time interval from 0 extrapolated to infinity
BA	Bioavailability
BI	Boehringer Ingelheim
BLQ	Below The Lower Limit Of Quantification
BMI	Body Mass Index
BWC	Bioavailability/Bioequivalence, Within-Subject Design, Time-Controlled
BWU	Bioavailability/Bioequivalence, Within-Subject Design, Time-Uncontrolled
CARE	Clinical Data Analysis and Reporting Environment
CI	Confidence Interval
Cmax	Maximum measured concentration of the analyte in plasma
CTP	Clinical Trial Protocol
CTR	Clinical Trial Report
CV	Arithmetic Coefficient of Variation
DB	Dose Proportionality, Between-Subject Design
DBLM	Database Lock Meeting
DG	Dose Group
ECG	Electrocardiogram
ECGPKS	ECG PK Set
eCRF	Electronic Case Report Form
EudraCT	European Union Drug Regulating Authorities Clinical Trials
gCV	Geometric Coefficient of Variation
gMean	Geometric Mean
HR	Heart Rate

Term	Definition / description
ICH	International Conference On Harmonisation
██████████	██████████
LLT	Lower Level Term
Max	Maximum
mRNA	Messenger Ribonucleic Acid
Mean	Arithmetic Mean
MedDRA	Medical Dictionary For Regulatory Activities
Min	Minimum
N	Number non-missing Observations
NC	Not Calculated
NOA	Not Analysed
NOP	No Peak Detectable
NOR	No Valid Result
NOS	No Sample Available
O*C	Oracle Clinical
PD	Pharmacodynamic(s)
PDS	Pharmacodynamic Set
PfOS	Powder For Oral Solution
PK	Pharmacokinetic(s)
PKS	PK Parameter Analysis Set
po	per oral
POC	Percent Of Control
PR	Pulse Rate
PT	Preferred Term
PV	Protocol Violation
qd	Quaque Die, Once Daily
QT	Time between start of the Q-wave and the end of the T-wave in an electrocardiogram
QTc	QT interval corrected for heart rate using the method of Fridericia (QTcF) or Bazett (QTcB)
R	Reference Treatment
RAGe	Report Appendix Generator system
REP	Residual Effect Period

Term	Definition / description
RPM	Report Planning Meeting
RS	Randomised Set
SAS®	Statistical Analysis System
SD	Standard Deviation
SOC	System Organ Class
SP	Sampling Point
SRD	Single Rising Dose
T	Treatment
T1/T2	Test treatment 1/2
Tb	Tablet
TS	Treated Set
TSAP	Trial Statistical Analysis Plan
ULN	Upper Limit of Normal
WHO-DD	World Health Organization Drug Dictionary
XPKISTAT	Library of SAS® Macros for PK analysis

3. INTRODUCTION

As per ICH E9 ([1](#)), the purpose of this document is to provide a more technical and detailed elaboration of the principal features of the analysis described in the protocol, and to include detailed procedures for executing the statistical analysis of the primary and secondary variables and other data.

This trial statistical analysis plan (TSAP) assumes familiarity with the Clinical Trial Protocol (CTP), including Protocol Amendments. In particular, the TSAP is based on the planned analysis specification as written in CTP Section 7 “Statistical Methods and Determination of Sample Size”. Therefore, TSAP readers may consult the CTP for more background information on the study, e.g., on study objectives, study design and population, treatments, definition of measurements and variables, planning of sample size, randomisation.

Study data will be stored in a trial database within the Oracle ClinicalTM (O*C) system.

Pharmacokinetic (PK) parameters will be calculated using Phoenix WinNonlinTM software (version 6.3, Certara USA Inc., Princeton, NJ, USA).

The statistical analyses will be performed within the validated working environment CARE, including SASTM (current Version 9.4, by SAS Institute Inc., Cary, NC, USA), and a number of SASTM-based tools (e.g., macros for the analyses of adverse event (AE) data or laboratory data; Report Appendix Generator system (RAGe) for compilation/formatting of the clinical trial report (CTR) appendices).

4. CHANGES IN THE PLANNED ANALYSIS OF THE STUDY

Analysis of dose proportionality will only be performed on the fasted dose groups receiving tablets because it is known from previous studies that Pharmacokinetics differ considerably for administration of Powder for Oral Solution (PfOS).

All other analyses as planned in the revised trial protocol (based on all amendments) will be performed and are described in more detail in this TSAP.

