3. DESCRIPTION OF DESIGN AND TRIAL POPULATION

3.1 OVERALL TRIAL DESIGN AND PLAN

This first-in-man trial will be conducted in healthy male volunteers at a single centre.

A total of 72 healthy male subjects is planned to participate in 10 sequential groups of 8 subjects each during the SRD part, and in a group of 12 subjects during the BA part. Within each dose group of the SRD part, 6 subjects will receive the active drug and 2 will receive placebo. In the BA part, 12 subjects will receive the active drug. The dose groups to be evaluated are outlined in Table 3.1: 1 below.

Table 3.1: 1 Planned dose groups

1 Respective reserve subject numbers will be provided for dose groups 1-7 and BA part

2 Intake of a standard continental breakfast prior to drug administration

3 Intake of a standard high-fat breakfast prior to drug administration

4 In DG 8 (400 mg/placebo with continental breakfast) and DG 9 (400 mg/placebo with high-fat breakfast) the same subjects will be included and treated with the same treatments (i.e. always with active or with placebo) for an intra-individual comparison of the two different diets (after washout period of at least 14 days)

SRD part

The first part of the trial, the SRD part, is designed as single-blind, partially randomised, and placebo-controlled within parallel dose groups. Only one dose is tested within each dose group. The groups will be treated consecutively in ascending order of doses. Each group is divided into 2 cohorts of 4 subjects each (3 on active drug and 1 on placebo). On the first study day within each dose group, the first cohort will be treated in a single-blind manner in the following order: first subject (active) followed at least 1 h later by the second subject (placebo) followed at least 1 h later by the third subject (active) followed at least 10 min later by the fourth subject (active).

If BI 730357 treatment is safe and showed acceptable tolerability in the first cohort, the subjects in the second cohort will be treated not earlier than 2 days later in a single-blind randomised manner. In the second cohort, a time interval of at least 10 min will be

Proprietary confidential information © 2017 Boehringer Ingelheim International GmbH or one or more of its affiliated companies

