3.2 DISCUSSION OF TRIAL DESIGN, INCLUDING THE CHOICE OF CONTROL GROUP

For single-rising dose trials, the design described in Section [3.1](#) is viewed favourable under the provision not to expose the subjects involved to undue risks since the main study objective is to investigate safety and tolerability of BI 730357 and the risk to subjects will be minimized by studying sequentially ascending doses. For safety reasons the first cohort of each dose level will be treated in a fixed treatment sequence (Active-Placebo-Active-Active). The dose level being investigated at any time will be known to subjects, but single-blind conditions regarding each subject's treatment (active or placebo) will be maintained for both cohorts of each dose level.

The disadvantage of this trial design is a possible observer bias with regard to the dose-depending effects as well as time effects, but it has the virtue of minimizing subject risk by sequentially studying ascending doses. As time-effects are expected to be small relative to the differences between the doses in the broad range investigated, unbiased comparisons between treatments can still be expected.

It is standard in trials involving healthy volunteers to include a placebo group as control for the evaluation of safety and tolerability. Each dose group consists of 8 subjects with 6 on active treatment, and 2 on placebo. The placebo control group includes all subjects of all dose groups treated with placebo. 6 subjects per active treatment group are in general considered as sufficient for the exploratory evaluation of pharmacokinetics.

For the BA part comparing bioavailability of BI 730357 following administration as tablet in the fasted state versus oral solution (PfOS) in fasted state as well as tablet in the fasted state versus tablet under fed conditions, the crossover design is viewed favourable due to its efficiency: since each subject serves as his own control, the comparison between the treatments is based on a comparison within subjects rather than between subjects. Thus the inter-subject variability is removed from the comparison between treatments [\[R94-1529\]](#). Blinding is not possible because the treatments are distinguishable.

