7.1.3 Model

SRD part:

The basic model for the investigation of dose proportionality will be a power model that describes the functional relationship between the dose and PK endpoints.

$$\exp(Y_{ij}) = \alpha' * \exp(X_i)^\beta * \varepsilon'_{ij}$$

The model consists of a regression model applied to log-transformed data under fasting conditions. The corresponding ANCOVA model includes the logarithm of the dose as a covariate.

Proprietary confidential information © 2017 Boehringer Ingelheim International GmbH or one or more of its affiliated companies

Together with $\alpha' = \exp(\alpha)$ and $\varepsilon'_{ij} = \exp(\varepsilon_{ij})$, taking natural logarithms converts this model to a linear form as follows:

$$Y_{ij} = \alpha + \beta * X_i + \varepsilon_{ij}$$

where

Y_{ij}	logarithm of the pharmacokinetic endpoint for subject j at dose level i; where $i = 1, 2, \dots, 7, j = 1, 2, \dots, 8$;
α	intercept parameter;
β	slope parameter;
X_i	logarithm of dose i;
ε_{ij}	random error associated with subject j at dose level i (assumed to be independent and identically normally distributed).

This equation can be fit as a linear regression model. Based on the estimate for slope parameter (β), a 2-sided 95% CI for the slope will be computed. Perfect dose proportionality would correspond to a slope of 1. The assumption of a linear relationship between the log-transformed pharmacokinetic endpoint and the log-transformed dose will be checked.

If dose proportionality over the entire dose range investigated cannot be shown, an attempt will be made to identify dose range(s), where dose proportionality can be assumed.

BA part: Investigation of relative bioavailability

Relative bioavailability is primarily to be determined on the basis of the parameters $AUC_{0-\infty}$ and C_{max} (cf. [Section 5.5](#)). Those parameters will be ln-transformed (natural logarithm) prior to fitting the model.

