7.5.2 Secondary endpoints

Assessment of dose proportionality (SRD part, tablet application under fasting conditions)

Dose proportionality of the PK endpoints $AUC_{0-\infty}$ and C_{max} in plasma of BI 730357 tablets under fasting conditions (dose groups C, D, E, F, and G) will be explored as a secondary analysis using the power model that describes the functional relationship between dose and PK endpoints. The basic model consists of a regression model applied to log-transformed data under fasting conditions. The corresponding ANCOVA (Analysis of Covariance) model includes the logarithm of the dose as a covariate.

The model is described by the following equation:

CTP:

$$Y_{ij} = \alpha + \beta * X_i + \varepsilon_{ij}$$

where

Y_{ij} logarithm of the pharmacokinetic endpoint for subject j at dose level i ;
where $i = 1, 2, \dots, 5$ $j = 1, 2, \dots, 6$,
 α intercept parameter;
 β slope parameter;
 X_i logarithm of dose i ;
 ε_{ij} random error associated with subject j at dose level i (assumed to be independent and identically normally distributed).

This equation can be fit as a linear regression model. Based on the estimate for slope parameter (β), a 2-sided 95% CI for the slope will be computed. Perfect dose proportionality would correspond to a slope of 1. The assumption of a linear relationship between the log-transformed pharmacokinetic endpoint and the log-transformed dose will be checked.

If dose proportionality over the entire dose range under fasting conditions investigated cannot be shown, an attempt will be made to identify dose range(s), where dose proportionality can be assumed.

This analysis will be accomplished by using the XPKISTAT macro (design DB), based on the PKS.

Intra-individual comparison of fed conditions (SRD part, DG 8 and 9 only)

The intra-individual comparison of fed conditions is primarily to be determined on the basis of the parameters $AUC_{0-\infty}$ and C_{max} . Those parameters will be ln-transformed (natural logarithm) prior to fitting the model.

The statistical model used for the analysis of $AUC_{0-\infty}$ and C_{max} will be an ANOVA (analysis of variance) model on the logarithmic scale. This model will include effects accounting for the following sources of variation: 'subjects' and 'treatment'. The effect 'subjects' will be considered as random, whereas the 'treatment' effect will be considered as fixed. The model is described by the following equation

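### Does limiting dose proportionality to fasted tablets, on the strength of unnamed previous studies, call for a change to the SAP?

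*SAP*

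**What the plan says.** Protocol 7.1.3 defines the dose-proportionality model for the SRD part: "The model consists of a regression model applied to log-transformed data under fasting conditions". The dose index runs from 1 to 7, and formulation is not mentioned. Protocol Table 4.1.4: 1 shows what the seven fasted levels are: oral solution (PfOS) at 2 and 8 mg, and tablets at 25, 50, 100, 200 and 400 mg.

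SAP section 4 lists a single departure from the protocol. Dose proportionality will use fasted tablet groups only, "because it is known from previous studies that Pharmacokinetics differ considerably for administration of Powder for Oral Solution (PfOS". SAP 7.5.2 carries this out: proportionality for "tablets under fasting conditions (dose groups C, D, E, F, and G) will be explored as a secondary analysis", with the dose index running from 1 to 5. Further down, the same section keeps a sentence from the protocol: "If dose proportionality over the entire dose range under fasting conditions investigated cannot be shown", the analysts will look for narrower ranges where proportionality can be assumed.

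Three other places bear on the stated reason:

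- Protocol 3.1: "This first-in-man trial will be conducted in healthy male volunteers at a single centre".
- Protocol 3.2 describes the bioavailability (BA) part as "comparing bioavailability of BI 730357 following administration as tablet in the fasted state versus oral solution (PfOS) in fasted state".
- Protocol section 11, amendment 3 (05 May 2017), used here for timing only: "Preliminary clinical data on safety, tolerability and PK from the SRD and BA part presented", and in its rationale "Since we observed a 36% increase in exposure in the fed versus fasted condition".

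The SAP is dated 22 September 2017.

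**The concern.** Three things make the change look doubtful.

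**The reason cannot be traced.** SAP section 8 has twelve references: guidelines, internal standards and one QT paper. None is a PK comparison of oral solution with tablet. In the public documents, the only such comparison in humans is this trial's own BA part.

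**The timing is awkward.** Amendment 3 revised the dose-proportionality text when preliminary PK was available, yet it kept seven levels. The SAP dropped two of them 140 days later. A reader could suspect that the levels were chosen after looking at the data.

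**The inherited range phrase no longer fits literally.** Dose groups 1 and 2 were also fasted, so the words could be taken to cover 2 to 400 mg when the model covers 25 to 400 mg.

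Dose proportionality is part of the stated secondary objective of the SRD part. If the restriction had discarded good information, or had been picked to obtain a favourable slope, the reported estimate would deserve less trust.

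**Working it through.** **Inputs.** Doses and formulations come from Protocol Table 4.1.4: 1. There are 6 active subjects per level (Protocol synopsis; SAP 7.5.2). The slope interval is two-sided 95%. The documents give no between-subject gCV, so 40% is assumed, with 30% and 60% as a range. They give no PfOS/tablet exposure ratio either, so 1.25, 1.5 and 2 are assumed.

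**Step 1: what leaves the model.** The protocol has 7 levels, 400/2 = 200-fold, 7 × 6 = 42 active subjects. The SAP has 5 levels, 400/25 = 16-fold, 5 × 6 = 30 subjects. Both counts agree with the index limits printed in the two documents.

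**Step 2: the apparent loss of slope information.** With x = ln(dose), Sxx is the sum of squared deviations of x over subjects.

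| Set | Sxx |
|---|---|
| Seven levels pooled | 123.40 |
| Five tablet levels | 28.83 |
| Within the two PfOS levels | 5.77 |

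The half-width is t(0.975, df) × sqrt(ln(1 + gCV²)) / sqrt(Sxx). At gCV 40% it is 0.070 for the pooled fit (df 40) and 0.147 for tablets only (df 28). On its face the interval doubles.

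**Step 3: why that comparison misleads.** The two lowest doses are exactly the two solution doses. If solution exposure is F times tablet exposure, the pooled slope shifts by ln(F) × cov(x, [PfOS]) / var(x) = -0.2236 × ln(F):

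- F = 1.25: -0.050
- F = 1.5: -0.091
- F = 2: -0.155

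At F = 1.5 the bias of 0.091 already exceeds the pooled half-width of 0.070. The narrower interval would be centred in the wrong place. The extra precision comes from treating the formulation contrast as a dose contrast.

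**Step 4: what an honest seven-level model gains.** A formulation term leaves only within-formulation information: 28.83 + 5.77 = 34.59 after rounding. The share of the lost information recovered is 5.77 / (123.40 - 28.83) = 6.1%.

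| Model, gCV 40% | 95% half-width |
|---|---|
| Tablet only (SAP), df 28 | 0.147 |
| Formulation term, common slope, df 39 | 0.132 |
| Separate slopes, tablet, df 38 | 0.145 |
| Separate slopes, PfOS | 0.32 |
| Difference between slopes | 0.36 |

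At gCV 30% and 60%, tablet-only gives 0.112 and 0.212, the common slope 0.101 and 0.191, and the slope difference 0.27 and 0.51. The common-slope gain of 10% depends on equal slopes, which a difference known only to ±0.36 cannot support. If the slopes were 0.7 for tablet and 1.0 for PfOS, the common estimate would be (28.83 × 0.7 + 5.77 × 1.0) / 34.59 = 0.75, off the tablet value. With separate slopes the tablet half-width narrows by 1%.

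**Step 5: timing.** From 05 May to 22 September 2017 is 26 + 30 + 31 + 31 + 22 = 140 days. The amendment shows that preliminary PK from both parts existed. The comparison it quantifies is fed against fasted; it gives no PfOS/tablet figure. Protocol 7.3.4 sends preliminary PK to the investigator and trial team by design, and Protocol 4.1.5.1 handles the database open-label.

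**Step 6: the range phrase.** It sits in SAP 7.5.2 under a heading confined to tablets under fasting conditions, after groups C to G are named and the index is set to 5. SAP Table 6.1: 1 maps C to G to 25 to 400 mg. In that context it means the modelled range.

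**The case for a change.** The best case for acting is that this is the only departure SAP section 4 lists, so its reason ought to be checkable, and it is not. The sponsor planned to pool all seven levels and kept that plan in amendment 3 with preliminary PK available. It changed course only afterwards. In a first-in-man trial the phrase about previous studies invites the question whether this trial's own BA part is meant. Naming the source would cost one line.

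What stands: the source is unnamed, and the documents do not show whether in-trial PK prompted the change. What does not stand is the inference that the analysis suffers. First-in-man describes the start of the trial. Other human data by September 2017 cannot be excluded, since amendment 3 already mentions a planned multiple-dose trial, and the protocol section holding the preliminary data is not in the public text. If the BA part was the source, a within-trial finding that the formulations differ would be a proper reason not to pool them. The dose layout supports the same choice without any PK. Protocol 7.2 treats the slope interval as exploratory, and no acceptance range is set for it, so there is no threshold that a choice of levels could be steered to meet.

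**Conclusion.** No change to the plan. The tablet-only slope is the right main estimate because formulation and dose do not overlap in the SRD part, and nothing raised here would alter it. The fall from 200-fold to 16-fold is real, but the precision apparently lost belongs to a pooled fit that would be biased unless the two formulations gave equal exposure. Against a model that respects formulation, the cost is a tablet half-width of 0.147 instead of 0.145, or 0.132 if a common slope is taken on trust. Those figures assume a gCV of 40%, and the biases assume exposure ratios of 1.25 to 2; neither is in the documents. The argument from non-overlap needs neither.

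The unnamed studies are missing detail in a declared change, which the authors of the trial report can fill by stating the source and the 25 to 400 mg range. The leftover range phrase is a clerical carry-over that the section's heading, groups and index already correct. A seven-level sensitivity model would add an analysis without useful information.
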